#### CONFIDENTIAL UNIVERSITY OF NORTH CAROLINA

**3.2.4** Active cardiac disease including any of the following:

- Severe congestive heart failure (class IV in accordance with the classification of the New York Heart Association)
- Unstable angina.
- Severe arrhythmia (i.e. ventricular tachycardia, flutter fibrillation; ventricular premature complexes occurring close to the preceding T-wave, multifocal complexes).
- Myocardial infarction within 14 days prior to the date of proposed Definity® administration.
- Uncontrolled systemic hypertension (systolic blood pressure (BP) >180 mm Hg and/or diastolic BP >100 mm Hg despite optimal medical management

**3.2.5** Is in an intensive care setting

**3.2.6** Has an unstable neurological disease (e.g cerebrovascular accident (including transient ischemic attacks (TIAs) within the 3 months before signing of informed consent

**3.2.7** Has undergone an invasive procedure on kidney lesion (e.g. tissue biopsy, surgery, nonsurgical cytoreductive procedure) since identification of lesion via US without contrast

**3.2.8** Has any other medical condition or other circumstances that would significantly decrease the chances of obtaining reliable data or of achieving the study objectives such as:

- Mental illness
- Drug abuse

**3.2.9** Female patient who is pregnant or lactating (the possibility of pregnancy has to be excluded by negative serum or urine B-HCG results, obtained within 24 hours before the perflutren lipid administration, or on the basis of patient history, e.g.: tubal ligation, hysterectomy or a minimum of 1 year without menses)

**3.2.10** Obesity that limits obtainment of acceptable images

#### CONFIDENTIAL UNIVERSITY OF NORTH CAROLINA

#### 4.0 STUDY PLAN

#### 4.1 Schema

Patients who meet study inclusion and exclusion criteria (see Sections 3.1 and 3.2) and provide informed consent will be subjected to a baseline conventional, non-contrasted ultrasound on Day 1. Following the non-contrasted ultrasound, CEUS will be performed on the identified lesion of interest. One year after initial study, a follow-up non-contrasted ultrasound will be obtained. The results of any other additional studies obtained clinically, including histology, contrasted or non-contrasted CT/MR, will be collected. Once all CEUS studies are completed, blinded radiologists will grade each lesion based on Bosniak criteria. Once all follow-up non-contrasted ultrasounds are obtained, radiologists will grade each lesion as stable, progressed, or regressed.

Please see the Time and Events Table in Appendix 2 for a full listing of evaluations and assessments throughout the course of the study.

#### 4.2 Study Design

#### 4.2.1 Patient Identification and Recruitment

Patients will be identified through UNC's nephrology, transplant and dialysis clinics. Additionally, community collaborators will be alerted to the study and asked for referrals. Patients who participated in the prior pilot study (LCCC 1219) with similar inclusion and exclusion criteria will be screened to determine if they still **CEUS CKD** PI: [name]

July 29, 2016

#### CONFIDENTIAL UNIVERSITY OF NORTH CAROLINA

meet criteria. The PI will communicate with the patient's referring clinician and the patient to determine whether they fit the inclusion/exclusion criteria and would like to participate in the study. The study coordinator will then be notified of these patients and approach the patient to further explain the study and obtain their signature on the informed consent form if they wish to participate. If patients consents, they will undergo perflutren-enhanced US. We will make every attempt to perform the perflutren-enhanced US during a regularly scheduled clinic visit. We will provide \$50 compensation and a parking voucher for completion of initial CEUS study. If two lesions are imaged, they will receive \$100. We will offer an additional \$50 for completion of all follow-up studies (6-month and 1-year urinalysis and serum creatinine and 1-year follow-up conventional ultrasound) and \$75 if they are not cared for at UNC and need to make an additional trip to UNC to obtain the studies. We plan on enrolling a total of 75 patients that fit the above criteria over a 6-month period.

Healthy volunteers will also be recruited at study initiation to optimize the imaging technique. These volunteers will receive equivalent compensation. In the case of any abnormalities found during the study, the subject will be informed of the finding, and the finding will be communicated to the subject's primary provider by study PI for further management.

Patients that decline enrollment will be asked if they would be willing to participate as controls. This would involve no CEUS study and only collection of serum creatinine levels over a 1-year follow-up period from the patient's primary provider.

#### 4.2.2 Multicenter sites.

Vanderbilt University (VU) will be a partnering institution participating in enrollment and imaging of patients on this trial. Affiliates will be subjected to the same protocol. Patients will be identified similarly through nephrology, transplant and dialysis clinics.

#### 4.2.3 Sonographic Evaluation

Study subjects will be asked to lie on an examination table in the UNC Radiology Department of US or at VU for the patients at the affiliate site. Once the patient is positioned, US gel will be applied to the patient's back or flank. The US imaging transducer will then be placed on top of the gel. Once the kidney lesion is located, the distance from the transducer to the nearest edge of the target lesion will be recorded. Pre-dose Doppler and B-mode investigations of the target lesion will be performed at baseline using commercially available US equipment and standard technique. Subsequent to this, either color or power Doppler imaging should be used to study the anatomy of the target lesion and surrounding vessels. Images (baseline and perflutren-enhanced) will be digitally recorded on a cine loop.

#### 4.2.4 Perflutren Administration

### CONFIDENTIAL UNIVERSITY OF NORTH CAROLINA

See http://www.definityimaging.com/pdf/VIALMIX%20Users%20Guide.pdf, and the package insert, for instructions on perflutren lipid preparation and activation. Peflutren lipid is intended for intravenous (IV) administration only after activation in the Vialmix® apparatus.

Resuscitative carts and trained personnel will be immediately available during Perflutren administration and imaging.

Perflutren will be administered in a continuous infusion using the dosing range and administration type within the perflutren prescribing information (see http://www.definityimaging.com/how-administration.html). If a subject has a central port 20 gauge or greater and does not have a filter then perflutren will be administered through the central port. If a subject does not have a central port then perflutren will be administered through the antecubital vein, preferably on their dominant hand.

Once perflutren lipid has been administered, the transducer is maintained in a constant position over the area of interest to show the target lesion and include some normal kidney, in order to assess the enhancement pattern during the early, mid and late vascular phases. Using flash-replenishment imaging approach, the contrast agent needs to be fully cleared from the tissue of interest to achieve accurate flow measurements. Imaging with perflutren lipid will be performed with software (Siemens Medical Solutions USA, Inc) using the flash-replenishment high-MI imaging technique. We will use sufficient MI to cause microbubble elimination, not to exceed 1.1.

The contrast-enhanced US examination will consist of the complete dynamic realtime assessment of the contrast enhancement profile of the lesion in comparison to the surrounding renal parenchyma. The flash-replenishment technique will allow the area of interest to be captured with multiple image sequences until the infusion dose is complete (approximately 5 – 6 minutes). If there are multiple lesions in one subject, the subject will have the option to undergo a  $2^{nd}$  contrast-enhanced study 30-minutes after the initial contrast dose, per dosing instructions in the package insert.

Upon completion of imaging study, the patient will be brought back to the radiology holding area and monitored by nursing staff for 30 minutes after study completion. Blood pressure and heart rate will be obtained 15 and 30 minutes post procedure and recorded on the flowsheet.

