#### 1.3.1 Background

Definity® (perflutren lipid) is an FDA-approved US contrast agent indicated to opacify the left ventricular chamber and to improve the delineation of the left ventricular endocardial border in patients with sub-optimal echocardiograms. It is activated by mechanical agitation with a Vialmix® which produces a milky white injectable suspension of perflutren lipid microspheres composed of octafluoropropane. Activated perflutren may be injected by either an intravenous bolus or infusion. See http://www.accessdata.fda.gov/scripts/cder/drugsatfda/ for full prescribing information when used in this indication. When used in this setting, the maximum dose of perflutren is administered as either two bolus doses or one single intravenous infusion.

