# CONFIDENTIAL UNIVERSITY OF NORTH CAROLINA

than 200,000 patients who received one of these contrast agents. In all those studies a composite rate of serious adverse events was calculated to be 1 - 3 in 10,000, compared to gadolinium-based MRI contrast which has an incidence of NSF of 2 - 5 in 100 patients with chronic kidney disease.

Following a meeting of the FDA Cardio-renal Advisory Committee in 2008, the black box warning was revised. The revisions shortened the contraindications to include cardiac shunts and hypersensitivity to perflutren and mandated the 30-minute monitoring period be limited to patients with pulmonary hypertension or unstable cardiopulmonary conditions. The black box warning was further revised in 2011, removing the mandatory 30-minute monitoring period, but stating that most serious cardiopulmonary reactions occur within 30 minutes of administration. For this reason, the label states that cardiopulmonary resuscitation personnel and equipment be readily available prior to perflutren administration, and that all patients be monitored for acute reactions.

Patients with a history of cardiac shunts, pulmonary hypertension or unstable cardiopulmonary conditions will be excluded from our study. In addition, all patients will be monitored for 30-minute post-perflutren administration by the research or clinical nurse or research physician.

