#### 6.2 Treatment Assessments

Subjects will be monitored for any untoward medical occurrences or toxicities from the time of signed informed consent through 30 minutes after perflutren lipid administration.

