#### 7.4.2 Individual Subject Stopping

Patient safety will be considered during the study intervention with individual patient withdrawal for criteria outlined in 4.4 and managed as described in 4.6. There are no subsequent interventions after the initial contrast-enhanced ultrasound.

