#### CONFIDENTIAL UNIVERSITY OF NORTH CAROLINA

follow-up period					
Patients declining CEUS but allowing creatinine follow-up 					
Serum creatinine	Х		Х	Х	Х

For any patients that do not complete the CEUS study, an ongoing adverse events/serious adverse events will be followed to the resolution of the event. For any patient that is deceased before the 1-year follow-up most recent creatinine levels and imaging studies will be collected and autopsy results documented, if available.

Comprehensive medical history obtained at time of enrollment; thereafter history focused on symptoms and assessments.

Consent can be obtained and signed at either screening visit or during the prestudy visit. It will always be reviewed at pre-study visit, even if signed during screening visit.

Women of childbearing potential must have negative urine or serum pregnancy test on the day of CEUS study, prior to the study.

Serum creatinine levels will be obtained clinically at the discretion of the patient's primary provider. We will obtain results of serum creatinine levels drawn by the primary provider.

Urinalysis will be obtained prior to and post CEUS study. This will be obtained by Radiology Nursing staff as per agreement. Results will be obtained and recorded by Study Coordinator. At approximate 6 and 12-month intervals, urinalysis will also be obtained. This can be done locally with results sent to UNC.

During the CEUS study, Study Coordinator will record time of injection.

Adverse event assessment will happen during the CEUS study and the 30-minute post-study monitoring period, where they will be monitored by the Radiology nursing staff with vital signs (blood pressure and heart rate) recorded in the hospital's electronic monitoring system. These results will be collected by the Study Coordinator and documented in the Monitoring Logs/Flowsheets housed in the Radiology Research Coordinator Office.

For patients who undergo biopsy or nephrectomy, tissue diagnosis will be requested after the procedure.

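### Section 4.2.4 offers a second perflutren infusion about 30 minutes after the first without stating a combined dose limit, where the interval starts, or a check before re-dosing (minor)

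*Combined protocol and SAP*

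**What the plan says.** **Dose.** Section 4.2.4 states: "Perflutren will be administered in a continuous infusion using the dosing range and administration type within the perflutren prescribing information". No volume, rate or total is given. For a patient with several lesions, the same section offers an optional second "contrast-enhanced study 30-minutes after the initial contrast dose, per dosing instructions in the package insert". Section 1.3.1 describes the labelled limit in the approved cardiac use: "When used in this setting, the maximum dose of perflutren is administered as either two bolus doses or one single intravenous infusion".

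**Monitoring.** Section 1.3.2 says that "all patients will be monitored for 30-minute post-perflutren administration by the research or clinical nurse or research physician". Section 6.2 has subjects watched for untoward events from consent "through 30 minutes after perflutren lipid administration". The end of section 4.2.4 starts nursing observation once the imaging study is complete and adds: "Blood pressure and heart rate will be obtained 15 and 30 minutes post procedure". Footnote 8 of Appendix 2 says: "Adverse event assessment will happen during the CEUS study and the 30-minute post-study monitoring period".

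**Stopping.** Section 4.4 allows withdrawal before the intervention is complete, for an unacceptable adverse event or for a change in the patient's condition as the investigator judges it. Section 4.2.1 sets a higher payment when two lesions are imaged, so the second study is a planned option.

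**The concern.** Two things are left for the sites to work out.

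The first is the total dose. The study uses infusions only, and section 1.3.1 describes the maximum as a single infusion. A reader at either of the two sites could take the insert's limit as applying to each study separately, or to both together. The text does not say which.

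The second is the interval between doses. Section 5.7 says that serious cardiopulmonary reactions typically arise within 30 minutes of administration, and section 1.3.2 commits the study to observation for that long. If the 30 minutes before re-dosing are counted from the start of the first infusion, the second dose begins before that observation is complete. Nothing expressly requires vital signs, or a look for a reaction, to be recorded before the second dose. What is at stake is a reaction to the first dose that goes unrecognised before a second is given, together with an unstated limit on the total dose.

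**Working it through.** The plan states no figure to reproduce here. The check sets the sections side by side and does simple arithmetic on time and dose.

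**Inputs.** Infusion length d is about 5 to 6 minutes, with imaging until the infusion ends (4.2.4). The interval to the second study is 30 minutes (4.2.4). Vital signs fall 15 and 30 minutes after the procedure (4.2.4). Observation lasts 30 minutes after administration (1.3.2). I assume that the procedure ends when the infusion ends. Time zero is the start of the first infusion.

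**Interval counted from the start of the first infusion.**
- Second dose starts at 30 minutes.
- Infusion-free gap = 30 − d: 30 − 5 = 25, or 30 − 6 = 24 minutes.
- Shortfall against 30 minutes of observation: 30 − 25 = 5, or 30 − 24 = 6 minutes.

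**Interval counted from the end of the first infusion.**
- Second dose starts at d + 30 = 35 to 36 minutes.
- Infusion-free gap = 30 minutes; no shortfall.

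**Timed vital signs due before the second dose, if the schedule applies after each study.** Sets fall at d + 15 = 20 to 21 minutes and d + 30 = 35 to 36 minutes.
- Second dose at 30 minutes: one set comes before it.
- Second dose at 35 to 36 minutes: two sets, the later one due just as the second dose starts.

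**The same, if the schedule applies once after the whole session.** No set is due between doses.
- Interval from start: the second infusion ends at 30 + d = 35 to 36, so the first set falls at 50 to 51 minutes.
- Interval from end: the second infusion ends at d + 30 + d = 40 to 42, so the first set falls at 55 to 57 minutes.

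The per-study reading is the more natural one. Section 4.2.4 itself calls the repeat a study, and observation begins when the imaging study is complete.

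**Dose.** Let each study use a fraction f of one maximum infusion. The documents give no dose, so f is assumed. Total = 2f.

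| f | Total, in maximum infusions |
|---|---|
| 0.5 | 1.0 |
| 0.75 | 1.5 |
| 1.0 | 2.0 |

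The total stays within one maximum only if f is 0.5 or less. The protocol does not state that condition.

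**The case against.** The strongest reply is that the label already governs. Section 4.2.4 ties dosing to it twice, once for the infusion and once for the second study, so any labelled limit on total or repeat dosing is brought in exactly where the option is offered. Section 1.3.1 is background for the cardiac setting, and nothing says that either infusion is at the maximum. This stands. A reader might infer that the protocol authorises an overdose, but the documents do not support that: two submaximal infusions may be within the label, and the insert is not among the documents. What remains is that the limit is not said to cover the two studies together, while the protocol's own summary leaves no room for a second full infusion.

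On timing, the dose in 4.2.4 is naturally the whole infusion, so the interval would run from its end and give a full 30 minutes. Even the shorter gap of 24 to 25 minutes exceeds the 1 to 15 minutes within which section 1.3.2 places the adverse events it describes with the discontinuations. That section also says the label no longer mandates 30 minutes of observation. These points reduce the risk, but they do not fix the starting point.

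A reader might also infer that patients go unobserved between doses. They do not. Sections 1.3.2 and 6.2 and footnote 8 all provide for observation, and 4.2.4 keeps resuscitation equipment and trained staff at hand. Section 4.4 lets the investigator withdraw a patient before a second dose. What is missing is narrower: a recorded check at that moment.

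Two further inferences fail. Section 7.4.2 says "There are no subsequent interventions after the initial contrast-enhanced ultrasound", which might look like a contradiction. However, the initial examination can mean the whole baseline session, as section 4.2.1 can be read, so this is wording only and needs no change. Build-up of gas is not supported as a worry either: section 1.3.2 reports a mean half-life of 1.3 minutes, though in only 8 healthy subjects.

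**Conclusion.** The point holds as a minor safety clarification. A second full infusion does not fit section 1.3.1, and the combined limit is not written out. Depending on where the interval starts, the infusion-free gap is 24 to 25 or 30 minutes, so at worst the second dose begins 5 to 6 minutes before the promised observation is complete. On the natural, per-study reading, one or two sets of vital signs fall due before re-dosing; the count is zero only if the schedule is read as applying once to the whole session. No check is expressly made a condition of the second dose.

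This rests on the stated infusion length, on the procedure ending with the infusion and, for dose, on an assumed f. The number of patients who would take the option is not given. The accuracy analysis is unaffected.

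**What to change.** In section 4.2.4:

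1. State that total perflutren over both studies may not exceed the labelled maximum for one infusion. If that is not workable, image the second lesion on another day.
2. Count the 30 minutes from the end of the first infusion, so that the observation promised in 1.3.2 is complete before any second dose.
3. Before a second dose, record blood pressure, heart rate and a check for reactions, and apply the section 4.4 withdrawal criteria.

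If the sponsor finds that the insert expressly allows a repeat infusion, section 1.3.1 should be corrected in place of item 1; items 2 and 3 would still apply.

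The cost is a few sentences and at most one extra set of vital signs per two-lesion patient. There would be no extra set where the 30-minute reading is already taken after each study, since it can serve as the check. The downside is that some second lesions would be imaged at a lower dose, later or not at all.

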#### 4.2.5 Assessment of Imaged Lesions

Two blinded radiologists at each institution (UNC and VU) will interpret the US images independently. Each interpreter will be asked to assess multiple lesion characteristics including echogenicity, size, septations, vascularity, and patterns of

enhancement which will be used to classify the lesion into a Bosniak category. A diagnostic conclusion (e.g. benign, malignant, or indeterminate lesion) will be derived based on the Bosniak category. Bosniak categories I, II and IIF will be classified as benign, and categories III and IV as malignant. The Bosniak classification system can be found in Appendix I.

Results of the perflutren-enhanced scans will not be used to dictate treatment and will not be shared with patients.

#### 4.2.6 Truth Standard

Because the majority of patients will not undergo surgery/biopsy or receive a contrasted CT or MRI, the truth standard will be the change from baseline non-contrasted US at one year follow-up non-contrasted US, the most typical clinical approach to these lesions. Follow-up US will be categorized as either stable, regression or progression. Lesions that are stable or have regressed will be deemed a negative test. Lesions that have progressed will be positive. When clinically indicated, if tissue pathology/biopsy or other imaging studies including contrasted CT or MRI are available, these will be collected and used in secondary analyses.

#### 4.3 Follow-up

For all patients, the treatment path will be decided by the subject's primary physician. We will review the medical records from each patient for a minimum of 12 months post CEUS and document results of 6-month and 1-year urinalysis and serum creatinine and follow-up non-contrasted US 12 months after CEUS. Additionally, any contrast-enhanced or non-contrast CT and/or MRI findings or surgical procedures performed as part of their routine standard of care will be collected and reviewed.

